6.3 Other Study Related Definitions

Analytical Study Week/Timepoint Assignments

Analytical windows will be used to assign parameter measurements to study weeks and time points. The algorithm is provided in Appendix A.

Actual Treatment Group

A subject's actual treatment group is the randomized treatment group, unless the subject receives treatment throughout the study that is different than the randomized treatment group assignment, in which case the actual treatment group is the treatment received.

Investigational Product (IP)

SC IP includes evolocumab SC 140 mg Q2W, evolocumab SC 420 mg QM and their corresponding SC placebo.

Study Exposure Period in Months (Double Blind)

For each randomized subject, Study Exposure Period = (EOS date – Randomization date + 1) / 365.25 * 12

SC IP Exposure Period in Months

For each Q2W subject:

SC IP Exposure Period = [min (Last SCIPD + 14 days, EOS Date) - First SCIPD + 1]/ 365.25 * 12

For each QM subject:

SC IP Exposure Period = [min (Last SCIPD + 28 days, EOS Date) - First SCIPD +1] / 365.25 * 12

Atorvastatin Therapy Exposure Period in Months

For each subject:

Atorvastatin Therapy Exposure Period = [min (Last POSTD + 1 day, EOS Date) – First POSTD + 1] / 365.25 * 12

Treatment-emergent Adverse Event (TEAE)

Treatment-emergent adverse events are adverse events occurring between the first dose of IP and EOS. Treatment emergent adverse events can be identified if the values of the AE eCRF question "Did event start before first dose of investigational product?" is No or missing.

Serious Adverse Event (SAE)

Treatment-emergent adverse events (as defined above) that are indicated as serious on the Adverse Events eCRF.

Target IP TEAE (On-treatment IP TEAE)

Target IP TEAEs are adverse events occurring during IP exposure period.

Reflexive Approach for LDL-C and VLDL-C

For all analyses related to LDL-C and VLDL-C, unless specified otherwise, a reflexive approach will be used. When calculated LDL-C is less than 40 mg/dL or triglycerides are > 400 mg/dL, the UC LDL-C value and UC VLDL-C value from the same blood sample will be used instead, if available.

Achievement of LDL-C < 70 mg/dL

A subject has achievement of LDL-C < 70 mg/dL if the post-baseline LDL-C value at week 12 is less than 70 mg/dL. If the value is missing, the subject is considered without the achievement.

Mean achievement of LDL-C < 70 mg/dL at weeks 10 and 12 is defined using the mean of non-missing LDL-C values at those two timepoints (if one is missing, mean equals the available one).

7. Analysis Subsets

7.1 Full Analysis Set

The full analysis set (FAS) includes all randomized subjects who received at least one dose of IP. This analysis set will be used in both efficacy and safety analyses. In efficacy analyses, subjects will be grouped according to their randomized treatment

group assignment, regardless of the treatment received. For safety analyses, subjects will be grouped according to their actual treatment group (as defined in Section 6.3).

7.2 Lipid Stabilization Analysis Set

The lipid stabilization analysis set (LSAS) includes all subjects enrolled who receive at least one dose of assigned atorvastatin. The LSAS will be used in safety summaries during the lipid stabilization period.

7.3 Completer Analysis Set

The completer analysis set (CAS) includes subjects in the FAS who adhered to the scheduled IP regimen and atorvastatin therapy (i.e. the SC, and atorvastatin completion boxes are checked on the eCRF), and have observed values for the co-primary endpoints. The completer analysis set will be used in sensitivity analyses of the co-primary endpoints.

7.4 Subgroup Analyses

Subgroup by stratification factors

- Statin therapy at study entry (no statin use vs non-intensive statin use vs intensive statin use [see Appendix C])
- Site's geographic region (China, South Korea, other countries)

Subgroup by baseline characteristics

- Age (< 65 years, \geq 65 years)
- Sex
- Race (black, white, and other)
- Baseline LDL-C (< median, ≥ median)
- Family history of premature coronary heart disease (yes, no)
- Baseline PCSK9 level (< median, ≥ median)
- Body Mass Index (BMI; < 25 kg/m², 25 < 30 kg/m², ≥ 30 kg/m²)
- Hypertension (yes, no)
- Current smoker (yes, no)
- Baseline CHD risk factors ≥ 2 (yes, no)
- Baseline triglycerides (< median, ≥ median; < 150 mg/dL, ≥ 150 mg/dL; < 200 mg/dL, ≥ 200 mg/dL)

8. Interim Analysis and Early Stopping Guidelines

No interim analysis is planned for this study.

An external independent DMC has been established to formally review the accumulating data from this and other completed and ongoing studies with evolocumab to ensure there is no avoidable increased risk of harm to subjects. The independent DMC is chaired by an external academic cardiologist who is an expert in lipids and clinical trials. Analyses for the DMC are provided by the Independent Biostatistical Group (IBG), which is external to Amgen. Details are provided in the DMC charter.

9. Data Screening and Acceptance

9.1 General Principles

The objective of the data screening is to assess the quantity, quality, and statistical characteristics of the data relative to the requirements of the planned analyses.

9.2 Data Handling and Electronic Transfer of Data

The Amgen Global Study Operations – Data Management (GSO-DM) department will provide all data to be used in the planned analyses. This study will use the RAVE database.

All data collected in the eCRF will be extracted from RAVE. Protocol deviations will be transferred from eClinical. Final PK data for all randomized subjects will be transferred from statistical programming to Amgen's CPMS group. Unblinded subject and box ID randomization lists will be provided by Amgen's randomization group and the IVRS/IWRS when the study stops. Details on data transfer will be provided in the Data Transfer Plan.

9.3 Handling of Missing and Incomplete Data

9.3.1 Patterns of Missing Data

Subjects may be missing specific data points for various reasons. In general, data may be missing due to a subject's early withdrawal from study, a missed visit, or non-evaluability of a data point or an endpoint at a particular point in time. In the Data Quality Review (DQR) process, queries will be made to the sites to distinguish true missing values from other unknown values (e.g. due to measurement or sample processing error). All attempts will be made to capture missing or partial data for this trial prior to the database lock.

The frequency and pattern of missing data for efficacy endpoints will be assessed through descriptive summaries of the measurements over time.

9.3.2 Missing Lipid Measurements

For efficacy endpoints, where the analysis method is repeated measures linear effects model, missing lipid measurements will not be imputed. A sensitivity analysis will be performed based on multiple imputation method for the co-primary endpoint. The handling of missing LDL-C response (achievement of LDL-C < 70 mg/dL) is provided in Section 6.3.

9.3.3 Handling of Incomplete Dates

Adverse event and concomitant medication with completely or partially missing start dates will be queried. After the issue is queried, if the date is still incomplete with year only or year and month only, the start date will be imputed as described in Table below.

	-		-
	Missing	Imputation	Exception
Start date (AE and concomitant	Day	1	Default to Study Day 1 if an event starts the same year and month as Study Day 1
medication)	Day / Month	1-Jan	Default to Study Day 1 if an event started the same year as Study Day 1

Table 1. Imputation Rules for Incomplete Dates

9.4 Detection of Bias

This study has been designed to minimize potential bias by the use of randomization of subjects into treatment groups and the use of blinding. Other factors that may bias the results of the study include:

- Major protocol deviations likely to impact the analysis and interpretation of the efficacy endpoints
- Subject level unblinding before final database lock and formal unblinding
- DMC related analyses

Important protocol deviations likely to impact the analysis and interpretation of the efficacy endpoints will be tabulated in the Clinical Study Report (CSR).

Any unblinding of individual subjects prior to formal unblinding of the study will be documented in the CSR. The impact of such unblinding on the results observed will be assessed.

Page 21

For DMC related analyses, details of access to subject level treatment assignments are provided in the protocol, Section 10.3.

Additional sensitivity analyses may be included to assess the impact of potential biases on the primary endpoint. If any sensitivity analyses are required to evaluate potential biases in the study's conclusions, then the sources of the potential biases and results of the sensitivity analyses will be documented in the CSR.

9.5 Outliers

Various methods, including univariate summaries, histograms, scatter plots, box plots, and line graphs, may be used to identify outliers in key safety and efficacy variables. Extreme data points will be identified during the blinded review of the data prior to database lock. Such data points will be reviewed with clinical data management to ensure accuracy. The primary analyses will include outliers in the data. Sensitivity analyses may be undertaken if extreme outliers for a variable are observed.

9.6 Distributional Characteristics

Distributional assumptions for the primary and secondary endpoints will be assessed. If the assumptions are not met, then alternative methods will be utilized. The use of alternative methods will be fully justified in the CSR.

9.7 Validation of Statistical Analyses

Programs will be developed and maintained, and output will be verified in accordance with current risk-based quality control procedures.

Tables, figures, and listings will be produced with validated standard macro programs where standard macros can produce the specified outputs.

The production environment for statistical analyses consists of Amgen-supported versions of statistical analysis software; for example, the SAS System version 9.3 or later.

10. Statistical Methods of Analysis

10.1 General Principles

The final analysis will be conducted when all subjects have either completed all the scheduled study visits or have early terminated from the study. At that time, the database will be cleaned, processed and a snapshot will be taken; the study will also be unblinded. Based on the snapshot, efficacy and safety analyses will be performed on the FAS. Unless specified otherwise, the FAS will be the default analysis set in this study and data will be summarized by randomized treatment group.

Analyses will be performed separately by each dose frequency (Q2W and QM) as two separate trials unless specified otherwise. Differences in model estimates between evolocumab QM and evolocumab Q2W and associated confidence intervals for the differences will be calculated for each lipid parameter. The superiority of evolocumab to placebo will be assessed for all efficacy endpoints. Unless specified otherwise, all other hypothesis testing will be 2-sided with a significance level of 0.05.

Subject disposition, demographics, baseline characteristics, and exposure to IP will be summarized.

Summary statistics for continuous variables will include the number of subjects, mean, median, standard deviation or standard error, minimum, and maximum. For categorical variables, the frequency and percentage will be summarized.

Multiplicity Adjustment Method

In order to preserve the familywise error rate at 0.05, each independent dose frequency (Q2W and QM) will be allocated a significance level of 0.05 for the co-primary endpoints. For FAS, methods of adjusting for multiplicity due to testing the superiority of evolocumab in combination with atorvastatin to placebo in combination with atorvastatin for both the co-primary and co-secondary efficacy endpoints within each dose frequency are described in the diagram below.

The testing strategy outlined in the diagram will be executed two times: once for each IP dose frequency for testing versus placebo. Within each IP dose frequency, testing of each co-endpoint pair will result in a single p-value (see Table 2 for more details), and for co-secondary endpoints these p-values will then be used in the Hochberg procedure. The following method will be used to preserve the family wise error rate for co-primary and co-secondary efficacy endpoints for testing within each IP dose frequency:

- If the treatment effect differences between evolocumab in combination with atorvastatin and placebo in combination with atorvastatin from the primary analysis of the co-primary endpoints are both significant at a significance level of 0.05, statistical testing of the tier 1 co-secondary efficacy endpoints (as defined in Section 4.1.2) will follow the Hochberg procedure at a significance level of 0.005 (Hochberg, 1988).
- If all tier 1 co-secondary efficacy endpoints are significant, the tier 2 co-secondary efficacy endpoints for evolocumab in combination with atorvastatin vs. placebo in combination with atorvastatin will be tested using the Hochberg procedure at a significance level of 0.025.
- 3. If not all tier 1 co-secondary efficacy endpoints are significant, the tier 2 co-secondary efficacy endpoints for evolocumab in combination with atorvastatin vs. placebo in combination with atorvastatin will be tested using the Hochberg procedure at a significance level of 0.02 (Wiens, 2003).

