10.2 Sample Size Considerations

The sample size is 300 subjects for each of the evolocumab SC in combination with atorvastatin arms, and 150 subjects for each of the placebo in combination with atorvastatin arms. The sample size should provide adequate power to determine the superiority of evolocumab in combination with atorvastatin to placebo in combination with atorvastatin as measured by the co-primary endpoints in both dose frequencies using the FAS. The primary analysis will require the tests of each co-primary endpoint to be significant at a level of 0.05 (Section 10.5). From the global phase 2 studies in the evolocumab program, the treatment effect measured as the mean of week 10 and week 12 were as large or larger than week 12 and highly correlated (> 85%) with ones at week 12. From the global phase 2 study 20110155, the treatment effects (on top of stable background statin therapy) of evolocumab compared to placebo for 140 mg Q2W and 420 mg QM in the mean percent change from baseline in LDL-C are -66.10 (95% CI [-71.48,-60.72]) and -50.33 (95% CI [-56.04,-44.62]) at week 12, respectively and the observed evolocumab dose group means in the type 2 diabetes mellitus cohort were comparable to the overall population. The power calculation is derived assuming a treatment effect in the percent reduction of LDL-C of at least 35% at week 12 in each dose frequency, with a common standard deviation (SD) of 20%. It is assumed that approximately 15% of subjects randomized into IP will end IP early, thus attenuating the treatment effects. It is assumed there will be no treatment effect differences among treatment groups after these subjects end IP early. After accounting for treatment attenuation due to early IP termination, the assumed treatment effect is a 30% reduction in LDL-C with a common SD of 30%. Assuming 2% of randomized subjects do not receive any IP, the planned sample size will provide at least 99% power in testing the superiority of evolocumab in combination with atorvastatin to placebo in combination with atorvastatin at week 12 in each dose frequency. Therefore, the sample size as planned will provide at least 98% (99% x 99%) power for the co-primary endpoints in each of the dose frequencies.

Since the testing statistics from the Q2W and QM groups are independent, there is approximately a 96% (98% x 98%) chance to show the superiority of both dose frequencies for the co-primary endpoints.

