10.4.2 Primary Analysis

The primary analysis will be conducted when all subjects have either completed all the scheduled study visits or have early terminated from the study. At that time, the database will be cleaned, processed and a snapshot will be taken; the study will also be unblinded. Based on the snapshot, efficacy and safety analyses will be performed on

the FAS. Unless specified otherwise, the FAS will be the default analysis set in this study and data will be summarized by randomized treatment group.

Analyses will be performed separately by each dose frequency (Q2W and QM) unless specified otherwise.

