10.5 Planned Methods of Analysis

General Considerations

Subject disposition, demographics, baseline characteristics, and exposure to IP will be summarized.

Summary statistics for continuous variables will include the number of subjects, mean, median, standard deviation or standard error, minimum, and maximum. For categorical variables, the frequency and percentage will be given.

Methods of handling missing data for efficacy endpoints will be described throughout this section. Missing data will not be imputed for safety endpoints.

Multiplicity Adjustment Method

In order to preserve the familywise error rate at 0.05, each independent dose frequency (Q2W and QM) will be allocated a significance level of 0.05. For FAS, methods of adjusting for multiplicity due to testing the superiority of evolocumab in combination with atorvastatin to placebo in combination with atorvastatin for both the co-primary and co-secondary efficacy endpoints for the co-primary endpoints within each dose frequency are described in the diagram below.

The multiplicity adjustment method for testing the co-primary and co-secondary efficacy endpoints within each dose frequency using the FAS is described below:

- If the treatment effect differences between evolocumab in combination with atorvastatin and placebo in combination with atorvastatin from the primary analysis of the co-primary endpoints are both significant at a significance level of 0.05, statistical testing of the tier 1 co-secondary efficacy endpoints (as defined in Section 10.1.1.2) will follow the Hochberg procedure at a significance level of 0.005 (Hochberg, 1988).
- 2. If all tier 1 co-secondary efficacy endpoints are significant, the tier 2 co-secondary efficacy endpoints for evolocumab in combination with atorvastatin vs. placebo in combination with atorvastatin will be tested using the Hochberg procedure at a significance level of 0.025.
- 3. If not all tier 1 co-secondary efficacy endpoints are significant, the tier 2 co-secondary efficacy endpoints for evolocumab in combination with atorvastatin vs. placebo in combination with atorvastatin will be tested using the Hochberg procedure at a significance level of 0.02 (Wiens, 2003).

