4.2 Planned Covariates

Baseline covariates include, but are not limited to:

Stratification factors

- Statin therapy at study entry (no statin use vs non-intensive statin use vs intensive statin use [see Appendix C]
- Site's geographic region (China, Korea, other countries)

Baseline characteristics

- Age
- Sex
- Race
- Baseline LDL-C
- Family history of premature coronary heart disease (yes, no)
- Baseline PCSK9

- Body Mass Index
- Hypertension (yes, no)
- Current smoker (yes, no)
- Baseline CHD risk factors \geq 2 (yes, no)
- Triglycerides

5. Hypotheses and/or Estimations

Hypothesis testing between IP treatment groups will be conducted separately by SC IP dose frequency.

The primary statistical hypothesis of the co-primary endpoints is as follows:

Within each randomized SC IP dose frequency, the null hypothesis is that there is no mean difference in the mean percent change from baseline at weeks 10 and 12 or in the percent change from baseline at week 12 in LDL-C between evolocumab and placebo in combination with atorvastatin QD, and the alternative hypothesis is that a mean difference does exist.

6. Definitions

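### Does testing each of two dose frequencies at 0.05 break the plan's statement that the familywise error rate is preserved at 0.05?

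*SAP*

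**What the plan says.** SAP 10.1 (Multiplicity Adjustment Method) begins: "In order to preserve the familywise error rate at 0.05, each independent dose frequency (Q2W and QM) will be allocated a significance level of 0.05", and adds that this level is for the co-primary endpoints. Protocol 10.5 has the same opening, "each independent dose frequency (Q2W and QM) will be allocated a significance level of 0.05", but without that limiter. There the limiter has slipped into the following sentence, which now reads oddly: "co-secondary efficacy endpoints for the co-primary endpoints within each dose frequency are described in the diagram below".

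On scope, SAP 10.1 says: "Analyses will be performed separately by each dose frequency (Q2W and QM) as two separate trials unless specified otherwise". It adds that the testing strategy is carried out twice, once per dose frequency, and that the method preserves the familywise rate for testing inside each frequency. SAP section 5 agrees: "Hypothesis testing between IP treatment groups will be conducted separately by SC IP dose frequency". Protocol 10.4.2 has the shorter form, "Analyses will be performed separately by each dose frequency (Q2W and QM) unless specified otherwise". Protocol 10.5 and the synopsis both describe the multiplicity adjustment as operating within each dose frequency.

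Within a frequency both co-primary endpoints must succeed. Protocol 10.2 puts it as "The primary analysis will require the tests of each co-primary endpoint to be significant at a level of 0.05", and SAP Table 2 implements it by comparing the larger of the two p-values with 0.05. Tier 1 then uses Hochberg at 0.005. Tier 2 follows at 0.02, or, if every tier 1 endpoint is significant, it "will be tested using the Hochberg procedure at a significance level of 0.025".

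**The concern.** A familywise rate belongs to a stated family. If the family is the whole study, giving the full 0.05 to each of two independent comparisons does not preserve 0.05, because nothing in the written steps splits alpha between the frequencies or requires both to win.

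Other features suggest that the study is one unit. The primary hypothesis (Protocol 2.6) names both regimens, and Protocol 10.2 and SAP 3.2 multiply power across frequencies (98% × 98% = 96%) with no matching step for type I error. The secondary levels, 0.005 + 0.02 = 0.025, also look like half of 0.05, although neither document says that this is the reason. A reader of the protocol alone does not find the SAP's two-trials wording, yet SAP section 11 reports no changes from the protocol.

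At stake would be the truth of the error-control statement for a phase 3 primary analysis.

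**Working it through.** **Inputs.** Level 0.05 per frequency (Protocol 10.5, SAP 10.1). Two-sided testing (SAP 10.1; SAP section 5 has a non-directional alternative). Larger p-value of the co-primary pair (SAP Table 2). Independent statistics for Q2W and QM (Protocol 10.2); each frequency has its own placebo arm (Protocol 3.1). Arms of 300 and 150, 2% never dosed, effect 30 and SD 30 percentage points after attenuation (Protocol 10.2).

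**1. The plan's 0.05 on the SAP's own scope.** Take one frequency.
- If at least one co-primary null is true, a false co-primary win needs that test to reject at 0.05, so the error is at most 0.05. Any secondary error needs the same gate to be passed, so the total stays at or below 0.05.
- If both co-primary effects are real and some tier 1 null is true, the error is at most 0.005 + 0.02 = 0.025.
- If both co-primary effects and all tier 1 effects are real, tier 2 error is at most 0.025.

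The familywise rate within a frequency is therefore at most 0.05, provided the Hochberg and union-intersection tests hold their stated levels. The plan's figure is reproduced.

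**2. The same rule counted study-wide.**
- Two-sided bound: 1 − (1 − 0.05)² = 0.0975.
- In evolocumab's favour only, 0.025 per frequency: 1 − (1 − 0.025)² = 0.0494.

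The first figure is a ceiling, approached when the two co-primary tests are almost perfectly correlated or when one of the pair has a real effect. When all four co-primary nulls are true, requiring both tests lowers it. The calculation uses a bivariate normal and takes the plan's correlation of more than 85% as the correlation of the test statistics, which is an assumption:

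| Correlation | Per frequency, p | Study-wide, 1 − (1 − p)² | Study-wide, favouring evolocumab |
|---|---|---|---|
| 0.85 | 0.0254 | 0.0501 | 0.0252 |
| 0.90 | 0.0296 | 0.0584 | 0.0294 |
| 0.95 | 0.0354 | 0.0696 | 0.0351 |

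**3. If the claim were that both regimens work.** With both null, both win falsely with probability at most 0.05² = 0.0025. With one null, the bound is 0.05. No split would be needed.

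**4. What a 0.025 co-primary threshold would do.**
- Study-wide two-sided bound: 1 − 0.975² = 0.0494.
- Numbers dosed: 300 × 0.98 = 294 and 150 × 0.98 = 147.
- SE = 30 × √(1/294 + 1/147) = 3.03. Noncentrality = 30/3.03 = 9.90.
- Smallest significant difference: 1.960 × 3.03 = 5.94 points at 0.05, and 2.241 × 3.03 = 6.79 points at 0.025.
- Power per test exceeds 0.9999 at either level. At half the planned effect (15 points) it is 0.9986 at 0.05 and 0.9966 at 0.025.

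**5. Protocol against SAP.** The operative levels (0.05 for the pair, 0.005 for tier 1, 0.02 or 0.025 for tier 2) are the same in both. The SAP adds words about scope and changes no analysis, so its section 11 statement stands.

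**The case for a change.** The best case for a change is that an error-rate statement should be true as written and mean one thing in both documents. The opening sentence carries no limit to one frequency and speaks of allocation to both, so read literally as a study-wide claim it is false. The protocol, the governing document, never states outright that the 0.05 applies per frequency. The documents also leave unsaid whether one winning frequency counts as study success, although the primary hypothesis names both regimens. Either repair is cheap: a few words, or a threshold of 0.025 with a negligible loss of power.

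Much of this stands as a comment on drafting. The sentence is imprecise, the limiter in Protocol 10.5 is in the wrong place, and the protocol would read better with the SAP's two-trials wording. It does not stand as a fault in the testing. The protocol sentence immediately after the disputed one, the paragraph after that, and the synopsis all confine the adjustment to each dose frequency, so the intended family can be recovered from the protocol alone. The stricter threshold is not a correction. The regimens differ in dose, interval and device and share no control arm, and statisticians reasonably differ on whether such comparisons must share alpha.

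**Conclusion.** The concern does not call for a change. On the family that the SAP declares, one per dose frequency, the familywise rate is held at 0.05, with the secondary tests using at most 0.025 once both co-primary effects are real. The 9.75% is correct arithmetic for a study-wide family that the SAP does not adopt. Even on that family, false claims favouring evolocumab are bounded at 4.94%.

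Clearer wording would alter no threshold, result or conclusion. A 0.025 threshold would raise the smallest significant difference from 5.94 to 6.79 points against a planned 30, so no co-primary conclusion is expected to differ. The rest is a clerical slip and a fair choice of family.

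This rests on independence of the two frequencies, on the plan's effect and SD assumptions, and on validity of the Hochberg and union-intersection tests at their levels. The testing diagram was not available to me, so the thresholds are taken from the written steps and SAP Table 2.
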